STUDY PROTOCOL

Official Title: Comparison of Bidirectional Palpation Test and Transit Time Flow Measurement for LIMA-LAD Graft Patency NCT Number: NCT06934993

Date: 11.10.2024

Sponsor Institution: Istanbul University-Cerrahpaşa, Faculty of

Medicine, Department of Cardiovascular Surgery

Ethics Approval: Approved by the Istanbul University-Cerrahpaşa Clinical Research Ethics Committee (approval dated 11.10.2024;

Turkish document added to the end of the file)

A. Rationale and Objective of the Study:

The aim of this study is to evaluate the correlation between the Bidirectional Palpation Test and TTFM measurements, and to assess early postoperative outcomes by examining graft patency using coronary CT angiography.

B. Main Study Form:

B.1.1. General Information:

Graft patency is one of the most critical factors determining morbidity and mortality after coronary artery bypass grafting (CABG). Revascularization of the left anterior descending (LAD) artery has been associated with improved long-term outcomes, including reduced mortality and relief of angina symptoms. The first-choice graft for LAD revascularization is the left internal mammary artery (LIMA). LIMA-LAD anastomosis is considered the gold standard due to its superior long-term patency.

Therefore, evaluating the patency of the LIMA-LAD anastomosis is crucial for both early and long-term outcomes. While various methods are used routinely, many are complex and costly. The bidirectional palpation test, developed in our clinic, is a subjective yet simple and reliable method. In this test, after completion of anastomoses, temporary weaning from cardiopulmonary bypass (CPB) is performed to establish pulsatile pressure. A segment of the LIMA with palpable pulse is identified. In the first step, a buildog clamp is placed distal to this point; continued palpation indicates antegrade flow from the subclavian artery. In the second step, the clamp is moved proximally; continued pulse detection indicates retrograde flow through the LIMA-LAD anastomosis, indirectly confirming its patency.

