Additionally, Transit Time Flow Meter (TTFM) measurements will be used as an objective method to evaluate graft patency. This study aims to assess the correlation between the bidirectional palpation test and TTFM with postoperative graft patency determined by coronary CT angiography. Within the first 30 postoperative days, coronary CTA will evaluate patency of the LIMA and other grafts, graft-native vessel calibration, graft position, sternum healing, and lung parenchyma.

B.1.2. Materials and Methods

B.1.2.1. Subjects Inclusion Criteria:

Patients planned for CABG in our clinic will be informed and consented. Those undergoing LIMA-LAD anastomosis will be included.

Exclusion Criteria:

Patients at risk for contrast nephropathy and those undergoing LAD revascularization with grafts other than LIMA will be excluded.

B.1.2.2. Methods Used in the Study

a. Laboratory and Clinical Assessment Methods:

Bidirectional palpation and TTFM measurements will be conducted intraoperatively using standard techniques, posing no additional surgical risk. Coronary CTA is selected as it is a non-invasive imaging method used to assess native coronary arteries and graft patency post-revascularization.

b. Statistical Methods:

Chi-square test, Student's t-test, Fisher's exact test, and Kaplan-Meier survival analysis for primary endpoints.

C. Protocol: C.1. Start Date of the Study: April 15, 2024

C.2. Duration of the Study:

6 months

C.3. Study Location:

Istanbul University - Cerrahpaşa, Cerrahpaşa Faculty of Medicine, Department of Cardiovascular Surgery

C.4. Study Investigators:

Advisors:

[name]. [name] Dr. [name]

Principal Investigator:

Dr. [name]

D. Study Outcomes, Ethics and Legal Requirements:

D.1. Outcomes:

This study is expected to reduce morbidity and mortality due to graft occlusion by allowing intraoperative assessment of graft flow and anastomosis quality. Revising the graft during surgery, if necessary, may prevent the risks and burden of reoperation. Additionally, if the bidirectional palpation test results are consistent with TTFM and early graft patency is confirmed via coronary CTA, this cost-free and easily applicable method may gain broader clinical adoption.

D.2. Ethics Committee Notification:

All necessary ethics committee notifications are planned before, during, and after the study.

D.3. Data Storage and Quality Assurance:

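### Protocol sections A and B.1.1 state the main comparison differently, and section D.1 can be read as supporting palpation without evidence that it detects a non-patent graft

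*Protocol*

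**What the plan says.** The protocol describes the purpose of the study in three places.

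- **Section A (rationale and objective).** "The aim of this study is to evaluate the correlation between the Bidirectional Palpation Test and TTFM measurements", followed by a second aim: "and to assess early postoperative outcomes by examining graft patency using coronary CT angiography". Palpation is paired with TTFM, and CTA supplies a separate early outcome.
- **Section B.1.1 (general information, last paragraph).** "This study aims to assess the correlation between the bidirectional palpation test and TTFM with postoperative graft patency determined by coronary CT angiography". The natural reading is that both intraoperative tests are related to CTA patency. The same paragraph calls TTFM an objective method; nowhere is it called the reference standard.
- **Section D.1 (outcomes).** Broader adoption of palpation may follow "if the bidirectional palpation test results are consistent with TTFM and early graft patency is confirmed via coronary CTA".

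The statistical methods line in B.1.2.2 b reads in full: "Chi-square test, Student's t-test, Fisher's exact test, and Kaplan-Meier survival analysis for primary endpoints". It names no primary endpoint, so it does not settle which comparison is the main one.

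**The concern.** D.1 presents intraoperative assessment as a way to recognise a graft that needs revision before the patient leaves theatre. The property that matters for that use is whether palpation picks out grafts that are not patent. The B.1.1 comparison addresses this. The section A comparison does not, because two tests can agree with each other and miss the same failures.

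D.1 joins agreement with TTFM to patency confirmed on CTA. If the second part means that CTA bears out each graft's palpation reading, D.1 matches B.1.1, but the wording does not say so. Read as an overall patency result, it is satisfied whenever nearly all grafts are open, whether or not palpation found the few that were not. An adoption statement could then rest on agreement and a high patency rate while detection is poor or unknown.

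The listed tests do not close this gap. A chi-square or Fisher p-value says that two classifications are associated; it does not give the share of non-patent grafts detected.

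**Working it through.** The protocol gives no sample size, expected non-patency rate or accuracy target, so there is no figure to reproduce. The counts below are assumed, and show only what is possible.

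**Assumptions.** 100 LIMA-LAD grafts; 5 non-patent and 95 patent on CTA; palpation and TTFM flag the same 4 grafts.

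**1. Palpation against TTFM (section A).** The table is [[4, 0], [0, 96]]. Agreement is 100/100, so kappa = 1. Fisher p = 1/C(100,4) = 1/3,921,225 = 0.00000026. CTA does not enter, so this holds whatever CTA shows.

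**2. Palpation against CTA (section B.1.1).** Let t of the 4 flagged grafts be non-patent. The table is [[t, 4−t], [5−t, 91+t]]; sensitivity = t/5 and specificity = (91+t)/95.

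| t | Sensitivity (exact 95% CI) | Specificity | Fisher p |
|---|---|---|---|
| 0 | 0% (0–52%) | 91/95 = 95.8% | 1 |
| 1 | 20% (1–72%) | 92/95 = 96.8% | 0.19 |
| 2 | 40% (5–85%) | 93/95 = 97.9% | 0.012 |
| 3 | 60% (15–95%) | 94/95 = 98.9% | 0.00024 |
| 4 | 80% (28–99%) | 95/95 = 100% | 0.0000013 |

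In every row palpation agrees perfectly with TTFM and 95% of grafts are patent, so the looser reading of D.1 is met. Sensitivity nevertheless runs from 0 to 80%.

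**3. Association is not detection.** At t = 2, Fisher p = [C(5,2)·C(95,2) + C(5,3)·C(95,1) + C(5,4)]/C(100,4) = (44,650 + 950 + 5)/3,921,225 = 0.012. The test against CTA is significant although 3 of 5 non-patent grafts are missed. This is a limit of the listed tests under either comparison, not a difference between the two.

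**4. The opposite direction.** Again 5 of 100 are non-patent. Palpation matches CTA exactly; TTFM flags 10 grafts, of which 1 is non-patent. Palpation against CTA has sensitivity and specificity of 100%. Palpation against TTFM has the table [[1, 4], [9, 86]]: observed agreement 0.87, expected agreement (5×10 + 95×90)/10,000 = 0.86, kappa = 0.01/0.14 = 0.07. The section A comparison can therefore also make a good test look poor.

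**5. Precision.** If all n non-patent grafts are detected, the exact 95% lower bound for sensitivity is 0.025^(1/n): 16% for 2/2, 48% for 5/5, 69% for 10/10. In 100 grafts with assumed non-patency of 2%, 5% or 10%, the binomial chance of 5 or fewer non-patent grafts is 98%, 62% or 6%. Unless failures are fairly common, sensitivity would be estimated imprecisely.

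**The case against.** The strongest reply is that nothing here is contradictory. One dataset can yield palpation against TTFM, each test against CTA, and the overall patency rate; no section excludes any of these. That stands. A reader might infer that the protocol contradicts itself, or that it omits the CTA comparison, and neither is so: B.1.1 plans it. What remains is that the aim is stated in two ways and no section says which one the conclusion rests on.

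Second, D.1 is prose about expected benefit, with no threshold or test. That also stands. A reader might take D.1 as a success criterion that lets palpation be adopted on agreement with TTFM alone. The text does not support this: it says only that adoption may follow, it mentions CTA as well, and it can be read in line with B.1.1. The firmer evidence is the difference between sections A and B.1.1; D.1 shows where the ambiguity could lead.

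Third, the counts are assumed, and the worst rows need both tests to flag the same wrong grafts. That is correct. The table shows that the comparisons can diverge, not that they will.

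Fourth, sensitivity, specificity and interval methods are often left to the SAP, which is not at hand, and listing some tests does not rule out accuracy estimates. Their absence from the protocol is therefore not counted as an error here. But an SAP should not have to choose between two differently worded aims in the protocol, and accuracy estimates are proposed only as the natural way to carry out the B.1.1 aim.

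**Conclusion.** The point holds as a matter of unreconciled aims. Section A makes palpation-TTFM correlation the first aim with CTA patency alongside; B.1.1 relates both tests to CTA patency; the protocol ranks neither. Under the looser reading of D.1, the data could appear to support palpation without showing that it detects a non-patent graft, and the listed association tests would not reveal this.

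The possible size, under the assumed 100 grafts with 5 non-patent and 4 flagged alike, is perfect palpation-TTFM agreement together with palpation sensitivity anywhere from 0 to 80%. No actual effect can be stated, because the protocol gives no counts. The change is worth making because it is cheap and uses data the trial already plans to collect, but it is not a fatal flaw. Confidence is medium, because D.1 admits a reading that agrees with B.1.1.

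**What to change.** 1. Align sections A and D.1 with B.1.1: CTA patency of the LIMA-LAD graft is the reference for both palpation and TTFM.
2. Report sensitivity for non-patency and specificity, for palpation and for TTFM, each with an exact 95% confidence interval. Make palpation-TTFM agreement (kappa) secondary.
3. Reword D.1 so that any adoption statement rests on palpation's accuracy against CTA and its interval, and is described as inconclusive if few non-patent grafts occur.
4. State whether CTA results were already known when the wording was changed. The protocol is dated 11.10.2024, and six months from the stated start of April 15, 2024 end on October 15, 2024, so some may have been. If so, the choice of reference and of the rule for claims is open to the criticism of being made after the fact, and disclosure lets readers judge that.

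The cost is in wording and analysis only: no extra patients, imaging or intraoperative steps. The downside is a more modest and possibly imprecise conclusion; even if every non-patent graft were detected, the lower bound for sensitivity would be only 16% with two such grafts and 48% with five.

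### D.1 ties wider adoption of palpation to conditions that never require it to detect a failed graft

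*Protocol*

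**What the plan says.** D.1 (Outcomes) first gives the reason for testing grafts in theatre, which is to allow correction before the chest is closed: "Revising the graft during surgery, if necessary, may prevent the risks and burden of reoperation". It then says what would support the palpation test: "if the bidirectional palpation test results are consistent with TTFM and early graft patency is confirmed via coronary CTA", in which case "this cost-free and easily applicable method may gain broader clinical adoption". What counts as consistent is not defined there.

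The cohort is described in B.1.2.1. "Patients planned for CABG in our clinic will be informed and consented", and "Those undergoing LIMA-LAD anastomosis will be included". The exclusions are risk of contrast nephropathy and use of another graft to the LAD. Nothing selects for grafts that are suspect or likely to fail. C.2 and C.3 give six months in one department. B.1.1 sets the timing of the imaging: "Within the first 30 postoperative days, coronary CTA will evaluate patency of the LIMA and other grafts".

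The protocol states no sample size and no expected rate of early LIMA-LAD failure. Its only remark on patency is qualitative and concerns the long term: "LIMA-LAD anastomosis is considered the gold standard due to its superior long-term patency".

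**The concern.** A test meant to prompt revision is useful only if it recognises an anastomosis that has failed. The harmful error is a palpable retrograde pulse in a graft that is not patent. D.1 is the only place where the protocol says what result would favour adoption, and it does not mention this error.

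- **Confirmed patency on CTA** is a property of the surgery. If the operations go well it is satisfied whatever palpation showed.
- **Consistency with TTFM** does involve palpation. But if it is read as the percentage of grafts on which the two methods agree, the result is driven by grafts that are normal on both.

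The enrolment is not enriched, the study is short, and grafts may be revised before CTA. All three point towards few failures in the data. The study could then report high agreement and full patency and be cited in favour of adoption, with little or no evidence on detection.

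**Working it through.** The protocol has no sample size, power or agreement target to reproduce. The figures below illustrate how D.1's wording would behave.

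**Inputs (all assumed, because the protocol gives none):** early failure rate p from 1% to 10%; number of patients N from 50 to 200; share of abnormal TTFM readings q from 2% to 15%.

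**1. A call of 'patent' for every graft, compared with CTA.**
- Observed agreement = 1 − p.
- Chance agreement = (1 − p) × 1 + p × 0 = 1 − p.
- Kappa = [(1 − p) − (1 − p)] / [1 − (1 − p)] = 0.
- Sensitivity for failure = 0; specificity = 1.
- Raw agreement is therefore 99%, 98%, 95% and 90% at p = 1%, 2%, 5% and 10%.

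**2. The same call compared with TTFM.** Raw agreement = 1 − q, which is 98% at q = 2% and 85% at q = 15%.

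**3. How many failures would be seen.** Expected number = N × p; chance of none = (1 − p)^N.

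| N | p | Expected failures | Chance of none |
|---|---|---|---|
| 50 | 1% | 0.5 | 0.61 |
| 50 | 2% | 1 | 0.36 |
| 50 | 5% | 2.5 | 0.08 |
| 50 | 10% | 5 | 0.005 |
| 100 | 1% | 1 | 0.37 |
| 100 | 2% | 2 | 0.13 |
| 100 | 5% | 5 | 0.006 |
| 100 | 10% | 10 | <0.001 |
| 200 | 1% | 2 | 0.13 |
| 200 | 2% | 4 | 0.02 |
| 200 | 5% | 10 | <0.001 |
| 200 | 10% | 20 | <0.001 |

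For example, 0.98^100 = 0.133, 0.98^50 = 0.364 and 0.95^100 = 0.006.

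**4. What a perfect result in few failures would show.** If all k failed grafts are flagged, the exact two-sided 95% lower limit for sensitivity is 0.025^(1/k).
- k = 1: 2.5%
- k = 2: 15.8%
- k = 3: 29.2%
- k = 5: 47.8%
- k = 10: 69.2%

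A lower limit of at least 70% needs k = 11, all flagged. To expect 11 failures takes 11 / 0.02 = 550 patients at 2%, 11 / 0.05 = 220 at 5% and 11 / 0.10 = 110 at 10%.

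**The case against.** A reader might infer more than this: that the cohort is bound to contain very few failures, that high agreement is therefore guaranteed, and that a test always reporting 'patent' would pass whatever statistic is used. The protocol does not support that reading, for four reasons.

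- **The failure count is unknown.** The patency statement in B.1.1 concerns the long term, not the first 30 days. With 200 patients and 5% to 10% failure, 10 to 20 failures would be expected.
- **The result depends on the statistic.** Section A and B.1.1 name correlation as the aim, and B.1.2.2 lists chi-square and Fisher's exact tests. A constant test has an undefined correlation and shows no association, so it would not succeed on those measures.
- **TTFM carries some information on detection.** An abnormal reading with a palpable retrograde pulse is a disagreement, and abnormal readings may be more frequent than non-patency on CTA.
- **D.1 is an expectation, not a success rule.** It says adoption may follow and makes no claim that palpation replaces TTFM. Accuracy measures may also stand in an analysis plan that is not shown, so their absence here is no fault.

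These points limit the claim but do not remove it. D.1 does not say that consistency means correlation or association. With no failures those measures cannot be computed, and with very few they say little, which leaves raw agreement as the easy basis for a claim. A significant association would not by itself show adequate detection. An analysis plan can add statistics, but it leaves the inference written in D.1 as it is.

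**Conclusion.** The point holds as a fault in the wording of D.1, in conditional form. Whatever the failure rate, the CTA condition does not test palpation, and neither condition requires that a failed graft be flagged. That both could be met by a test with no discriminating ability rests on two further assumptions: few failures, and consistency judged by raw agreement.

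The likely number of failures is uncertain. Within the assumed ranges, the chance of seeing none runs from 61% (50 patients, 1%) to below 0.1% (for example 100 patients, 10%). It should not be stated as fact that the cohort will contain almost no failures. The change is worth making because it alters what may be concluded at almost no cost.

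**What to change.** Reword D.1 so that any statement on adoption rests on palpation's detection of failed grafts, reported in two separate comparisons:

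- (a) against abnormal TTFM at the first reading, before any revision;
- (b) against non-patency on CTA, in grafts that were not revised.

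For each, give the number failed, the number flagged by palpation and the exact 95% confidence interval, next to the agreement that a call of 'patent' for every graft would have reached. List revised grafts separately with what prompted the revision.

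The two comparisons should not be pooled. Pooling would mix the comparator (TTFM) with the reference (CTA). Counting revised grafts as failures would build palpation into its own reference wherever palpation prompted the revision.

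State also that, if failed grafts are too few to exclude poor detection, the conclusion is limited to agreement in patent grafts, with no claim that palpation detects failure. Three of three flagged, with a lower limit of 29%, would be such a case.

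The cost is a few sentences in D.1, one table, and a record of the first TTFM reading and the reason for each revision. No extra patients are needed. The downside is a more modest permitted conclusion. The change adds no failures, and comparison (b) may have fewer still because revised grafts leave it.
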